 - the re-introduction of mavodelpar for subjects who had a break in mavodelpar treatment in studies REN001-101 or REN001-201; and
 - the introduction of mavodelpar for mavodelpar-naïve nDNA subjects.
- from the start of REN001-201. These presentations will focus on reporting Groups 1, 2, 3 and 4a and include data collected in both REN001-201 and REN001-202, except Group 4a, where only REN001-201 data will be included. This will continue to acknowledge the randomization to treatment groups at the start of the REN001-201. It will provide an insight on the influence of a 6-month delay in beginning mavodelpar on subject safety and efficacy outcomes. Importantly, this will summarize the data for all subjects randomized and dosed in REN001-201.
- from the start of REN001 treatment. These presentations will focus on reporting Groups 1, 2, 3 and 4 and include data collected in both REN001-201 and REN001-202 depending on when mavodelpar is initiated. This provides an overall summary of emergent data following the initiation of mavodelpar treatment to mtDNA-PMM

subjects. This is particularly important with respect to safety data (e.g., overall incidence of AEs with mavodelpar treatment).

For further details on the reporting groups refer to [Section 8.2](#).

The purpose of this SAP is to ensure that the data listings, summary tables and figures which will be produced, and the statistical methodologies that will be used, are comprehensive and appropriate for the assessment of study objectives specified in the study protocol. Changes from the analyses specified in the protocol will be identified in the SAP and any amendments to the SAP will be made prior to database lock. The SAP will be the point of reference for the analyses performed for the CSR. Any additional analyses not described in the final SAP or deviations from the final SAP will be documented in the CSR.

The SAP has been developed based on REN001-202 Protocol Version 3.0 and the latest CRF available (Version 6.0, Date 24 April 2023) and REN001-201 Protocol Version 4.0. The subsequent country specific protocol amendments for REN001-202 (see [Appendix 1](#)) do not impact the SAP.

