2.1. RESPONSIBILITIES

Veramed is the Biostatistics vendor for this study and is contracted to prepare the table, figures and listing (TFLs) shells based on this SAP. These shells will detail the format and layout of TFLs and will be presented in a separate document to the SAP. Veramed will perform the statistical analyses and is responsible for the production and quality control of all TFLs.

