7.2. SAFETY ANALYSIS SETS

There will be a separate safety set for each of the approaches for summarizing the data.

- from the start of REN001-202 – will include all REN001-202 subjects who signed the REN001-202 informed consent form, completed screening and received at least one dose of mavodelpar study medication in REN001-202.
- From the start of REN001-201 – will include all subjects who signed the REN001-201 informed consent form, completed screening and received at least one dose of study medication in REN001-201.
- from the start of REN001 treatment – will include all subjects who signed the informed consent form (REN001-201 form for mavodelpar REN001-201 subjects and REN001-202 form for REN001-201 placebo subjects), completed screening and received at least one dose of mavodelpar study medication in either REN001-201 (mavodelpar subjects in REN001-201) or REN001-202 (placebo subjects in REN001-201).

The ‘from the start of REN001-201’ safety analysis set summaries will be based on the actual treatment received. The safety analysis sets will be used for all baseline and safety analyses.

A listing safety analysis set will be used for listings. This will include all subjects who signed the informed consent form and received at least one dose of study medication in either REN001-201 or REN001-202.

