8.2. GENERAL METHODS

Continuous variables will be summarized using the number of non-missing observations (n), mean, SD, median, minimum, and maximum. Categorical variables will be summarized using counts and percentages.

Unless otherwise specified, the estimated mean and median for a set of values should be displayed to 1 more decimal place than the original values, and SD should be displayed to 2 more decimal places than the original values. The minimum and maximum should be displayed to the same number of decimal places as the original values. Deviations from this convention may arise to take account of the relevance of the precision (e.g., the distance walked in the 12MWT is reported to the nearest cm, but there is no relevance in presenting the mean to the nearest mm). These deviations from convention will be documented in the relevant analysis sections below.

Percentages will be displayed with 1 decimal place; except percentages will not be presented when the count is zero and 100% will be presented as an integer. Unless stated otherwise, percentages of subjects will be based on the number of subjects with non-missing data in the analysis set used for the presentation.

Unless stated otherwise, an on-treatment measurement will be any measurement collected (including scheduled and unscheduled visits) up to the date of last dose plus one day. Drug interruptions will not be considered, i.e., data will not be excluded during a drug interruption if the subject resumes study treatment; this includes the follow-up period for subjects who enrol in REN001-202 at the REN001-201 FU.

In by-visit summary tables, the baseline will be summarized using all available data, but also for each visit using only the baseline data from subjects with available data at the visit; hence the mean change from baseline will equal the mean observed visit value – mean baseline value.

Throughout this document ‘change from baseline’ refers to the actual change from baseline (i.e., observed visit value – baseline value). The baseline definitions are detailed in [Section 8.6](#).

There will be 3 approaches to summarising the data and, unless stated otherwise, all presentations will be presented for each approach. [Figure 1](#) in [Section 2](#) shows the different pathway options a subject can enter REN001-202 and the 5 distinct reporting groups these

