subjects represent. These 5 reporting groups are referenced in square brackets alongside the descriptions below. The summaries are:

- From the start of REN001-202 Summaries will be presented by mutation group (REN001 100 mg mtDNA-PMM [Groups 1 to 4] and REN001 100 mg nDNA-PMM [Group 5]). The mtDNA-PMM group will also be split by:
 - Placebo > REN001 100 mg [Group 1] – subjects who received placebo in REN001-201 and enrolled at REN001-201 W24, FU or after exit.
 - REN001 100 mg > REN001 100 mg [Group 2] – subjects who received mavodelpar in REN001-201 and enrolled at REN001-201 W24 visit.
 - REN001 100 mg >FU> REN001 100 mg [Group 3] – subjects who received mavodelpar in REN001-201 and enrolled at REN001-201 FU visit.
 - REN001 100 mg >Exit> REN001 100 mg [Groups 4a and 4b] – subjects who received mavodelpar in REN001-201 and enrolled after exiting REN001-201 or subjects who took part in REN001-101 study.

Summaries will extend out to Month 48, where applicable.

- From the start of REN001-201 which will be split by REN001-201 treatment group (REN001 100 mg [Groups 2, 3 and 4a] and placebo [Group 1]). Subjects who enrol in REN001-202 at REN001-201 Exit will only have their REN001-201 data included in these summaries. Baseline summary tables (disposition, demography, baseline characteristics, medical history and prior medications) will also include an overall summary.

Summaries will extend out to Month 54, where applicable, for all subjects who complete both studies.

- From the start of REN001 treatment [Groups 1, 2, 3 and 4]. Subjects who enrol in REN001-202 at REN001-201 Exit and receive mavodelpar in REN001-201 [Group 4a] will be counted as 2 separate subjects. Summaries will be presented over all subjects (REN001 100 mg).

Summaries will extend out to Month 54, where applicable, for subjects who receive mavodelpar in REN001-201 and enrol in REN001-202 at REN001-201 W24 or FU; for all other subjects summaries will extend to Month 48.

In addition, for summaries from the start of REN001 there is only Week 2 (Month 0.5), Week 18 (Month 4.5), Month 1 (Month 7) and Month 3 (Month 9) for subjects who receive mavodelpar in REN001-201 and therefore this visit will not be included in the by visit summaries. Refer to [Section 3.8](#) for diagram of visit assignment.

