9. ANALYSIS OF DISPOSITION, DEMOGRAPHIC AND BASELINE CHARACTERISTICS, AND MEDICATION

9.1. SUBJECT DISPOSITION AND WITHDRAWALS

To account for all pathways into REN001-202 a summary including REN001-201 and REN001-202 disposition will be generated. For REN001-201 the summary will be split by REN001-201 treatment groups and present the number (%) of subjects who were:

- Dosed in REN001-201 (% not required)
- Discontinued treatment in REN001-201 (along with reasons)
- Completed treatment in REN001-201 and did not enrol in REN001-202

Percentages will be based on the number of subjects dosed in REN001-201.

For REN001-202 the summary will be split by REN001-101 subjects, nDNA-PMM subjects, and the 6 REN001-201 enrolment pathway options:

1. REN001-201 REN001 enrolled at W24 visit
2. REN001-201 REN001 enrolled at FU visit
3. REN001-201 REN001 enrolled after exiting
4. REN001-201 Placebo enrolled at W24 visit
5. REN001-201 Placebo enrolled at FU visit
6. REN001-201 Placebo enrolled after exiting.

The summary will present the number (%) of subjects who were:

- Screened (for subjects who enrolled after exiting REN001-201, REN001-101 subjects or nDNA-PMM subjects)
- Rescreened (applicable for subjects who enrolled after exiting REN001-201, REN001-101 subjects or nDNA-PMM subjects)^a
- Not dosed in REN001-202^a
- Dosed in REN001-202^a
- Completed REN001-202^b
- Withdrew from REN001-202 (along with reasons)^b
- Ongoing in REN001-202 (applicable for interim analyses of REN001-202)^b
- In each analysis set (safety, FAS, PK and DXA)^b

^a Percentages will be based on the number of subjects in the REN001-202 screened set for subjects who enrolled after exiting REN001-201, REN001-101 subjects or nDNA-PMM subjects.

^b Percentages will be based on the number of subjects dosed in REN001-202.

The number (%) of subjects in the FAS and safety analysis sets will also be summarized from the start of REN001-201 and the number (%) in the safety analysis set from the start of REN001 treatment. The denominator will be based on the number of subjects dosed in REN001-201 and the number of subjects dosed with mavodelpar respectively.

For each scheduled visit the following number (%) of subjects will be presented for each safety analysis set:

- Who attended the visit
- Who missed the visit
- Who withdrew from the study prior to the visit

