- If a stop date is missing the day information and month/year is same as last study date then use last study date, else last day of the given month will be used for the stop day; if a stop date is missing the day/month and year is the same as last study date then use last study date, else December will be used for the stop month.

Only TEAEs will be included in the summary tables. Summaries will be generated for all TEAEs. Summaries will be presented overall and split by time period looking at AEs reported (based on AE start date) in the first month (up to and including Day 28), 2-6 months (Day 29 to Day 168 inclusive), 6-12 months (Day 169 to Day 336 inclusive) and >12 months (after Day 336). Summaries will be repeated for the subgroups – age (<65 years or ≥65 years), sex and race.

An overall summary will present the number and percentage of subjects with:

- any TEAE
- any TEAE considered as related to study drug (evaluated by the investigator as Possibly Related or Related)
- any TESAE
- any TESAE considered as related to study drug
- any AESI
- maximum severity TEAE of mild, moderate, or severe; i.e. a subject with TEAEs at different intensities will be summarized at the most severe intensity
- maximum severity for TEAE considered as related to study drug
- any TEAE leading to study drug discontinuation
- any TEAE leading to death

The table will include the total number of TEAEs reported. The total number of unique terms within subjects will also be presented, counting each TEAE PT only once within each subject.

The number and percentage of subjects with TEAEs will be presented by System Organ Class (SOC) and PT. Subjects with multiple TEAEs within a SOC or SOC/PT combination will be counted only once for that SOC or SOC/PT combination. Similar summaries will be presented for related TEAEs, AESI and TESAEs.

SOC and PT summaries of TEAEs by maximum severity (mild, moderate or severe) will be presented.

All summaries will be ordered by descending frequency of total number of subjects within each SOC and then similarly by decreasing frequency of total number of subjects within each PT, in the REN001 treatment group (i.e., from start of REN001-201 and from start of REN001 treatment this will be the REN001 100 mg group, and from start of REN001-202 this will be the mtDNA PMM Overall REN001 100 mg group). In cases of SOCs or PTs with equal frequencies, AEs will be sorted alphabetically.

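### TEAE percentages are split over periods of 28 to 1008 days or more with no exposure-adjusted rate and no at-risk denominator, so read at face value they mislead on whether risk changes over time

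*SAP*

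**What the plan says.** SAP 12.1 presents TEAEs as the number and percentage of subjects, each counted once per SOC or SOC/PT, together with a total event count. On time it says: "Summaries will be presented overall and split by time period looking at AEs reported (based on AE start date) in the first month" (Days 1-28), followed by Days 29-168, Days 169-336 and everything after Day 336.

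Section 12.1 gives no denominator for these periods. The general rule in SAP 8.2 is that "percentages of subjects will be based on the number of subjects with non-missing data in the analysis set used for the presentation", and SAP 12 assigns the safety evaluations to the safety analysis sets. Neither SAP 12 nor Protocol 8.6 plans a person-time rate for adverse events.

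SAP 2 explains why the presentation from the start of REN001 treatment exists: "This is particularly important with respect to safety data (e.g., overall incidence of AEs with mavodelpar treatment").

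The SAP does use risk-set denominators elsewhere. The blood-pressure categories in 12.4 are based on subjects still on treatment, and the interim attendance table in 9.1 is based on subjects who could have reached the visit. Neither rule is carried over to adverse events.

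**The concern.** Long-term safety is the primary objective and adverse events are the primary endpoints. A table of TEAEs by time period invites one question: does risk rise, fall or stay level as treatment continues? Two features stop the percentages from answering it directly.

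- **Period length.** The last period is 36 times as long as the first (1008/28), or 42 times with data to Month 54 (1176/28). A longer window collects more subjects with an event at the same risk.
- **Denominator.** For a period that a subject never reached, the SAP does not say what non-missing data means. If the whole safety set is used, withdrawn subjects and, at the interim, subjects not yet that far along stay in the denominator and pull late percentages down.

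The two effects work in opposite directions, so the net direction cannot be read from the table. An interim report for the regulatory submission is planned (SAP 13), and there the second effect is largest in relative terms.

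**Working it through.** The plan has no sample-size, power or event-rate figure to reproduce. The inputs from the documents are day counts.

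**Period lengths.** Boundaries are Days 28, 168 and 336 (SAP 12.1). Month 48 is Day 1344 (Protocol 6.13), so the last period is 1344 − 336 = 1008 days. For subjects on mavodelpar in REN001-201 who continue to Month 54, 168 + 1344 = 1512 and 1512 − 336 = 1176 days.

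**Step 1: complete follow-up.** Every subject is then in every denominator, so the denominator question drops out. With a rate r per 100 patient-years and L days, the percentage with at least one onset in the period is 100 × (1 − exp(−r × L / 36525)). For r = 10 and L = 1008 the exponent is 10 × 1008 / 36525 = 0.276, which gives 24.1%. All rates are assumptions.

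| Assumed rate per 100 patient-years, by period | Days 1-28 | 29-168 | 169-336 | 337-1344 |
|---|---|---|---|---|
| 10 throughout | 0.8% | 3.8% | 4.5% | 24.1% (27.5% over 1176 days) |
| 20, 10, 5, 2.5 | 1.5% | 3.8% | 2.3% | 6.7% |
| 40, then 10 | 3.0% | 3.8% | 4.5% | 24.1% |

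A constant risk looks like a steep rise. An eightfold fall puts the highest percentage in the lowest-risk period. A fourfold excess in month 1 still leaves month 1 lowest.

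**Step 2: interim cut.** Assume a constant 10 per 100 patient-years and entry to REN001-202 spread evenly over the 18 months before the cut (18 × 30.4375 = 547.9 days).

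- *Start of REN001-202.* The share reaching Day 337 is (547.9 − 336) / 547.9 = 38.7%. Averaging the formula over their follow-up gives 2.9% of those at risk, or 1.1% of the whole set. Whole-set percentages for the four periods are 0.7, 3.1, 2.4 and 1.1%.
- *Start of REN001 treatment* (equal arms, all roll over). Whole-set percentages are 0.8, 3.4, 3.1 and 2.3%, with 4.2% of those at risk in the last period.
- *Entry over 12 or 24 months instead.* Last period, whole set versus at risk: 0.03 vs 0.4% and 2.8 vs 5.2% (start of REN001-202); 0.7 vs 2.4% and 4.2 vs 6.5% (start of REN001).

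The same constant risk that looked like a rise in Step 1 now looks like a fall after month 6 in both 18-month cases.

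**Step 3: final analysis, start of REN001-202.** With h = 10/36525 per day and loss hazard k = −ln(1 − annual loss)/365.25, the last-period value among those at risk is h/(h + k) × (1 − exp(−(h + k) × 1008)). The whole-set value multiplies this by exp(−336k). Whole set versus at risk is 19.1 vs 21.1%, 14.9 vs 18.3% and 11.3 vs 15.7% at assumed losses of 10, 20 and 30% a year.

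**Step 4: can a reader undo this from other planned tables?** SAP 9.5 bands treatment duration by month to 3 months and then by 84 days. If a month is 28 days, band edges fall on Days 28, 168 and 336. Subject counts from the AE tables, divided by person-time rebuilt from band midpoints, were compared with true rates of 20, 10, 5 and 2.5. With 18 months of entry the result is about 20, 10, 5 and 2.4. With 12 months of entry the last period gives 0.9 instead of 2.5, because few subjects have passed Day 336 and the band midpoint overstates their follow-up.

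**Step 5: does the proposed rate work?** In a simulation of 1,000,000 subjects with 18 months of entry and true rates of 20, 10, 5 and 2.5, the by-period rates came out at 20.0, 10.0, 5.0 and 2.5 per 100 patient-years.

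**The case against.** The strongest reply is that the information is not lost. The duration bands are kept at the interim (SAP 9.5), and SAP 9.1 promises attendance tables: "For each scheduled visit the following number (%) of subjects will be presented for each safety analysis set". All AEs are listed with onset day, and with complete follow-up the formula in Step 1 can simply be inverted. This stands. A reader might infer that the plan makes a time trend impossible to recover; Step 4 shows that this goes too far. What remains is that the reader must do the calculation, and that it is least reliable for the last period at an early interim.

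A reader might also infer that the plan has no denominator at all. SAP 8.2 read with SAP 12 most naturally gives the whole safety set. The table shells may settle the wording: "These shells will detail the format and layout of TFLs and will be presented in a separate document to the SAP". That leaves a poorly suited denominator rather than an absent one, and nothing in the SAP asks the shells to lay out a rate.

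It is also fair to say that the study is descriptive, that unequal periods are visible from their labels, that no objective asks explicitly about a time trend, and that the SAP does not say which AE tables enter the synoptic interim report. In each 18-month case in Step 2 the denominator choice moves the percentage by less than 2 points. These replies limit the severity. They do not make the percentages comparable across periods.

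Finally, periods counted from the start of REN001-202 are not time on mavodelpar for Groups 2 and 3, who already have about 24 weeks of it. This is correct and is built into the fix.

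**Conclusion.** The concern holds as a matter of presentation. The planned time split shows percentages over windows that differ 36- to 42-fold in length, with a denominator that by default ignores who is still observed, and it plans no exposure-adjusted rate. Taken at face value it can point the wrong way even with complete follow-up: 24.1% against 0.8% at constant risk, and 6.7% against 1.5% when the true rate has fallen eightfold. Period length is the main cause. The denominator matters most in relative terms at the interim (1.1 vs 2.9% in the 18-month example), and at the final analysis only through withdrawal.

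The sizes rest on assumed event, entry and loss rates, because the documents give none; they illustrate direction and are not forecasts. Rates can be roughly rebuilt from other planned tables, so this is a cheap improvement and not a failure of the safety analysis. No hypothesis test or sample size is touched.

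**What to change.** Amend SAP 12.1 as follows.

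1. **Denominator.** For each period, use the subjects still under AE observation at its start, and print that N.
2. **Rates.** For any TEAE, TESAE, AESI and TEAE leading to discontinuation, add subjects with a first event per 100 patient-years with a 95% CI, overall and by period. By period, count the first event within that period and only the person-time within it. Person-time ends at the first event, last study contact or data cut, whichever comes first.
3. **Which presentation answers the question.** Name the start-of-REN001 presentation, whose safety set is built on subjects who "received at least one dose of mavodelpar study medication in either REN001-201 (mavodelpar subjects in REN001-201") or in REN001-202, as the one that measures time on mavodelpar. In the start-of-REN001-202 presentation, show rates by reporting group and note the roughly 24 weeks of earlier mavodelpar in Groups 2 and 3.
4. **Special cases.** State that the gap for subjects enrolling at the REN001-201 follow-up visit counts as AE observation time. This agrees with the measurement rule in SAP 8.2 ("Drug interruptions will not be considered, i.e., data will not be excluded during a drug interruption if the subject resumes study treatment"), but SAP 9.5 subtracts the same gap from days on treatment, so the difference should be explicit. Group 4a subjects "will be counted as 2 separate subjects" in the start-of-REN001 presentation. Let each record contribute its own person-time, and note that the two are not independent, so the interval is approximate there.

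The cost is SAP wording, an end-of-observation date per record, modest extra programming and wider tables. The dates needed are already collected.

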3.2 Endpoints

3.2.1 Primary Endpoints

For mtDNA and nDNA subjects:

- Number and severity of adverse events (AEs)
- Number of AEs leading to study drug discontinuation
- Number of serious adverse events (SAEs)
- Number of adverse events of special interest (AESI)
- Number of AEs leading to death

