8.6 Safety Analyses

No imputation will be used for handling missing data, with the exception of conservative approaches taken for missing AE information (e.g., intensity). Details of such conventions will be documented in the SAP.

Treatment-emergent adverse events will be summarized by SOC and Preferred Term, in accordance with the MedDRA coding dictionary. The number of subjects reporting each AE preferred term will be tabulated for all TEAEs and separately for those considered as at least possibly related to study treatment by the Investigator. Number of subjects reporting SAEs and AESIs will also be tabulated.

Changes from baseline in laboratory parameters (including bone and calcium markers), vital signs, ECG and eye examinations data will be summarized by visit.

The incidence of potentially clinically significant laboratory and ECG values (e.g., increase in QTcF ≥ 30 msec from baseline or an absolute QTcF value of ≥ 500 msec).

Absolute values and changes from baseline for the DXA endpoints will be summarized. Summaries will be presented over all subjects and for the following demographic sub-groups:

- Men
- Pre-menopausal women
- Post-menopausal women

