3.2. STUDY ENDPOINTS

3.2.1. Primary Endpoints

- Number and severity of Adverse Events (AE)
- Number of AEs leading to study drug discontinuation
- Number of serious adverse events (SAE)
- Number of adverse events of special interest (AESI)
- Number of AEs leading to death

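### All five primary endpoints are worded as numbers of events, but SAP 12.1 specifies an event total only for all TEAEs; SAEs, AESIs and AEs leading to discontinuation or death are tabulated only by subject

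*SAP*

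**What the plan says.** The five primary endpoints are the same in Protocol 3.2.1 and SAP 3.2.1, and each is a count of events. The first covers AEs of any kind and adds their severity. The second is worded "Number of AEs leading to study drug discontinuation". The third and fifth use the same form for SAEs and for fatal AEs. The fourth reads "Number of adverse events of special interest (AESI").

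SAP 12.1 sets out the tables:

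- **Overall summary.** The rows cover TEAEs, TESAEs, AESIs, TEAEs leading to discontinuation and TEAEs leading to death, and the unit is the subject: "An overall summary will present the number and percentage of subjects with" each of these. Severity enters as the subject's worst grade.
- **Event total.** "The table will include the total number of TEAEs reported". A second count takes each preferred term once per subject, which removes repeats of the same term.
- **SOC and preferred-term tables.** A subject counts once per SOC and once per SOC/PT combination. The AESI and TESAE tables follow the same pattern.
- **Listings.** All AEs are listed, with SAEs and AESIs flagged. TESAEs, AESIs and discontinuation TEAEs have a separate listing, and any deaths are listed with the associated AEs.

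Protocol 8.6 first plans the number of subjects reporting each preferred term and then adds: "Number of subjects reporting SAEs and AESIs will also be tabulated". SAP 14 declares no changes from the protocol's planned analyses.

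**The concern.** Long-term safety is the primary objective, and the primary endpoints are its formal expression. If the SAP is followed as written, the report will have a table of how many subjects had an SAE or an AESI, but none of how many SAEs or AESIs there were.

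The two numbers separate when events recur. The AESIs are muscle-injury laboratory changes with clinically significant AEs, cataract formation or worsening, and fractures (Protocol 7.1.1.5). Fractures and muscle injury can happen more than once in a subject, and presentations run to Month 48 or Month 54 (SAP 8.2). In the overall AESI row, a subject with one fracture and a subject with three contribute the same. Similarly, the tables do not show how many TEAEs were severe, only how many subjects had a severe one as their worst.

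**Working it through.** **Step 1: endpoint against specified output.** The plan states no event target, rate, alpha or powered sample size, so there is no figure to reproduce. The check is a comparison of text.

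| Primary endpoint (Protocol and SAP 3.2.1) | Event total specified in SAP 12.1? | What is tabulated |
|---|---|---|
| AEs, number | Yes, all TEAEs | Events and subjects |
| AEs, severity | No | Subjects, by worst grade |
| AEs leading to discontinuation | No | Subjects |
| SAEs | No | Subjects |
| AESIs | No | Subjects |
| AEs leading to death | No | Subjects |

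All five endpoints are numbers of events. One has an event total. Four do not, and the severity part of the first is by subject only.

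**Step 2: where the units can differ.** A subject who discontinues study treatment is withdrawn (Protocol 6.9 and 6.13), and death occurs once. For these two endpoints, events exceed subjects only if several AEs are attributed to one discontinuation or one death. SAEs and AESIs can recur freely, so the gap is mainly there.

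**Step 3: size, for illustration.** Inputs: N = 150, the expected mtDNA-PMM enrolment (SAP 3.5). The mean number of events per subject, m, is assumed, because the documents give no rates. Expected events = N × m. Expected subjects with at least one event:

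- Poisson: N × (1 − e^(−m))
- Gamma-Poisson with shape k = 0.5, where events cluster in some subjects: N × (1 − (1 + m/k)^(−k))

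| m | Events | Subjects, Poisson | Subjects, gamma-Poisson | Subject count below event count |
|---|---|---|---|---|
| 0.05 | 7.5 | 7.3 | 7.0 | 2% to 7% |
| 0.3 | 45 | 38.9 | 31.4 | 14% to 30% |
| 1.0 | 150 | 94.8 | 63.4 | 37% to 58% |

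For example, at m = 0.3, Poisson gives 150 × (1 − 0.741) = 38.9, and (45 − 38.9)/45 = 14%. Gamma-Poisson gives 150 × (1 − 1.6^(−0.5)) = 31.4, and (45 − 31.4)/45 = 30%.

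**Step 4: the same on a yearly scale.** With full follow-up to Day 1344, T = 1344/365.25 = 3.68 years. Poisson counts at assumed rates of 0.05, 0.10, 0.25 and 0.50 per subject-year and N = 150 give 27.6, 55.2, 138.0 and 276.0 events against 25.2, 46.2, 90.2 and 126.2 subjects. The shortfalls are 8.7%, 16.3%, 34.6% and 54.3%. The percentages do not depend on N.

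**The case against.** A reader might infer that repeat SAEs and AESIs are never counted, or that the recurrent burden is hidden. The documents do not support that. Every repeat treatment-emergent event is in the overall TEAE total, and the listings show the events one by one with SAEs and AESIs flagged. The tables also do not collapse everything: a subject with two different AESI preferred terms appears under each, and the summaries are split into four time periods by AE start date. Only repeats of the same term within one period vanish from those tables. This stands, with two limits. The TEAE total does not separate SAEs or AESIs from the rest. The last period is everything after Day 336, which is (1344 − 336)/1344 = 75% of planned REN001-202 follow-up.

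A reader might also infer that the SAP departs from the protocol without saying so. It does not. In Protocol 8.6 the SAE and AESI sentence extends a subject-level tabulation, so the protocol's own analysis is by subject and SAP 12.1 follows it. The entry of no changes in SAP 14 is consistent on this point. The conflict is between the endpoint wording and the analysis, and it begins in the protocol.

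Further points on the other side are fair. The study is descriptive, with no testing and no statistical basis for its size. If the events are rare, the two counts nearly agree. Worst severity per subject is a legitimate summary in its own right. The table shells are a separate document (SAP 2.1) that was not available and may already show event counts. However, they are to be based on the SAP, which does not require such counts.

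**Conclusion.** The point holds as a mismatch of unit. Four of the five primary endpoints have no specified table in the unit in which they are defined, and severity of AEs is given by subject only. The information is collected and listed, so nothing is lost, but tallying a listing is not a prespecified summary of a primary endpoint.

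It matters for SAEs and AESIs and little for discontinuation or death. The size cannot be fixed from the documents. On the assumed means of 0.05 to 1.0 events per subject, it ranges from a difference of half an event or less in 7.5 to more than half of the events. The upper figures need both frequent events and strong clustering. No inference changes.

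**What to change.** In the overall summary of SAP 12.1, print the number of events beside the number (%) of subjects for TESAEs, AESIs, TEAEs leading to discontinuation and TEAEs leading to death. Add the number of TEAEs at each severity, with each event counted at its own grade. An event column in the AESI and TESAE SOC/PT tables would be useful but is optional, since no endpoint requires it.

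Alternatively, reword the primary endpoints as numbers of subjects in both the protocol and the SAP and record the change in SAP 14. That resolves the conflict equally well but gives up the count of repeat events.

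The first route costs a few lines of SAP text and an extra column in existing tables. Severity, seriousness and action on study drug are already recorded for each event (Protocol 7.1.1.8.2), so no new data are needed, and SAP section 2 allows amendment up to database lock. The second route costs a protocol amendment.
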